8.3 SAMPLE SIZE DETERMINATION

The concept of a minimally important difference (MID) for depression rating scales are not yet widely established. However, both researchers and a growing number of clinicians who are using measurement-based care employ standardized symptom rating scales to determine whether treatments for depression and other conditions are working effectively (Rush et al., 2021). The degree of symptom improvement that is meaningful

Sponsor Name: Woebot Health

Protocol Number: WB001-001

to patients remains unclear. However, a recent analysis based on Brexanolone, an FDA-approved PPD-specific treatment based on HAM-D, provided the first estimates of PPD-specific MID and meaningful change threshold (MCTs) for the HAM-D in this clinically important outcome. It concluded that a 2–3 point change in the HAM-D6 is clinically meaningful and a 4–7 point change is clinically substantial (Rush et al., 2021). A second analysis based on two randomized controlled trials in 482 adult patients with MDD suggested a 2-point difference on the HAM-D6 will allow detection of a change in depression category as mild and moderate and defined as a scores of 8–9 and 10–12, respectively (Ruhe et al., 2005). Thus, as an adjunct to TAU, a 3-point change was identified as an a priori clinically meaningful difference for WB001 to demonstrate a reduction of depression for mild and moderate PPD (for additional justification for use of the HAM-D6 as the primary endpoint see Section 9.1 Primary Endpoint).

[REDACTED]

Simulations using this RCT study data were conducted to determine the power of various sample sizes to detect a 3-point difference in HAM-D6 score between the treatment and control groups at Week 8, controlling for relevant baseline factors and considering potential for additional variability within the study.

[REDACTED]

9. STATISTICAL METHODS

9.1 PRIMARY ENDPOINT

The HAM-D is considered the gold standard assessment in clinical trials of major depression, including pharmacotherapy trials in post-partum depression (Hantsoo, et al., 2014). Consequently, as PPD is considered a

Sponsor Name: Woebot Health

Protocol Number: WB001-001

subtype of major depression in the DSM-5, the HAM-D was considered the most appropriate primary endpoint. A recent comparative, post hoc analysis of the HAM-D17 and the abbreviated HAM-D6 in the GUIDED trial for MDD treatment found greater sensitivity differences in the treatment effects using the HAM-D6 scale (Dunlap et al., 2019). It was noted that as a multidimensional (or multifactorial) scale the HAM-D17 is good for detecting a broad array of clinical features, it also may reduce the ability to detect change over time, because some factors may not adequately distinguish groups when valid differences exist (Ruhe et al., 2005).

[figure not shown]
The importance of maximizing signal detection through use of the most sensitive scale to detect treatment effects is of great importance for comparative effectiveness studies. Particularly in a PPD population this provided justification for using the HAM-D6 scale (over the HAM-D17) that more narrowly and precisely measures the “core symptoms” of major depressive disorder according to DSM-5 criteria. The structural validity (unidimensionality) and measurement properties of the HAM-D6 have been well validated (e.g., O'Sullivan et al., 1997; Licht et al., 2005; Bech et al., 2009; Timmerby et al., 2017) and studies comparing the responsiveness of the HAM-D6 and HAM-D17 generally showed that the effect size of treatments was substantially larger according to HAM-D6 versus the HAM-D17 (Timmerby et al., 2017). Further, in studies where symptom reduction was used as an outcome measure, the HAM-D6 detected statistically significant differences between treatment groups more often than HAM-D17 (e.g., Feiger et al., 2006; Bech et al., 2022). Similarly, when remission or relapse rates constituted the outcome measure, HAM-D6 was generally found to be more sensitive than HAM-D17 in detecting differences between treatment groups (e.g., Rasmussen et AL., 2003; Thase et al., 2011).

Thus, for this study, the primary efficacy endpoint is the difference between treatment arms in the HAM-D6 score at Week 8 after controlling for baseline and other covariates. For the ITT population, a restricted maximum likelihood (REML) based linear mixed-effects model for repeated measures (MMRM)-approach will be used to test for systematic differences in change between arms over time, after accounting for participant -specific heterogeneity in HAM-D scores residual error structure. The MMRM will be parameterized to include random effects for site and repeated measures for post-baseline visits using an unstructured residual covariance structure (3 parameters); in the unlikely event that the unstructured covariance matrix fails to converge, the model will be refit with a first order autoregressive covariance matrix (2 parameters).

Sponsor Name: Woebot Health

Protocol Number: WB001-001

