- Change from baseline in Clinical Global Impression-Improvement (CGI-I) the CGI-Severity (CGI-S) at Week 4 and Week 8
- Change from baseline in Patient Global Impression-Change (PGI-C) and Patient Global Impression-Severity (PGI-S) at Week 4 and Week 8
- Client Satisfaction Questionnaire-8 at Week 8

Safety Endpoints: C-SSRS and Adverse Events (AEs), Serious Adverse Events (SAEs)

Safety Aim: To evaluate the safety of [WB001+TAU] versus [ED001+TAU] based on PI and Sponsor determined AE and SAEs. The study will use the Columbia-Suicide Severity Rating Scale (C-SSRS), the PHQ-9 item #9, and the EPDS item #10, and the HAM-D17 item #3 to facilitate identification of AEs and SAEs. It would be separately determined whether identified AEs or SAEs are related to the device.

Statistical Methods: The primary efficacy endpoint is the difference between treatment arms in the HAM-D6 score at Visit Week 8 after controlling for baseline and other covariates. For the ITT population, a restricted maximum likelihood (REML) based linear MMRM approach will be used to test for systematic differences in change between arms over time, after accounting for participant-specific heterogeneity in HAM-D6 scores residual error structure. The MMRM will be parameterized to include random effects for site and repeated measures for post-baseline visits using an unstructured residual covariance structure (3 parameters); in the unlikely event that the unstructured covariance matrix fails to converge, the model will be refit with a first order autoregressive covariance matrix (2 parameters).

Sponsor Name: Woebot Health

Protocol Number: WB001-001

This test will be performed using the final, MMRM model-based t-test with a two-sided significance level of 5%. Estimated least squares means for change from baseline and the observed absolute values (\pm SE) at each visit by treatment group will be plotted over time.

No explicit imputation will be performed; the MMRM model described above will be run on this population, which implicitly imputes missing data under a missing at random (MAR) assumption.

As a sensitivity analysis for the primary analysis using ITT population, MMRM model in the same manner as described above will be conducted in the PP population.

The treatment effectiveness on MIBS, EPDS, PHQ-9, and GAD-7 (difference between arms at Week 8, controlling for baseline) will be evaluated using the same analysis plan proposed for the analysis of the primary endpoint (HAM-D6).

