4.1 INCLUSION CRITERIA

A participant will be eligible for entry into the study if all the following inclusion criteria are met:

1. Participants must have primary residence in the United States
2. Participant must be willing to comply with all study procedures and restrictions
3. Participants must be able to understand and be willing to provide informed consent
4. Participants must be ≤ 92 days postpartum at the time of screening
5. Participants must be women aged 22-45 years who had onset of a major depressive episode during pregnancy or within 4 weeks following delivery according to DSM-5 diagnostic criteria (Segre et al., 2013)

Sponsor Name: Woebot Health

Protocol Number: WB001-001

- 7. Participants must own or have regular access to a smartphone (Android or iOS smartphone with a recent, supported operating system), and has reliable Wi-Fi access or sufficient data plan to engage with assigned treatment condition for the duration of the study
- 8. Participants must have current mild-moderate depression as measured by the HAM-D6 score > 7 and < 13 at Screening (Bech et al., 2007; Pridmore et al., 2020)
- 9. Participants must confirm having a form of TAU, defined as clinician supervised outpatient care management and includes follow-up visits, medication, psychotherapy, or some combination thereof.
- 10. As part of TAU during the study, any confirmed concomitant medications and psychotherapy are permissible and must be regularly scheduled or stable (i.e., dose and frequency, respectively) for over 4 weeks prior to BL visit

4.2 EXCLUSION CRITERIA:

A participant will not be eligible for study entry if any of the following exclusion criteria are met:

- 1. Gestation less than 28 weeks
- 2. HAM-D6 score, ≤ 7 or ≥ 13 (severe depression) at Screening
- 3. Currently pregnant or plans to become pregnant within the next 8 weeks
- 4. History of drug and/or alcohol use disorder within the past 12 months as measured by the SCID-5-CT
- 5. Lifetime history of suicide attempt or ideation with a plan and intent to harm oneself during the current episode of PPD
- 6. Current or lifetime psychosis, including history of post- or peri-partum psychosis as measured by the SCID-5-CT (Williams JB, 2015)
- 7. Current or lifetime history of schizophrenia, schizoaffective disorder, bipolar disorder, and/or homicidal or infanticidal ideation as measured by the SCID-5-CT

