9.2 SECONDARY ENDPOINTS

The treatment efficacy of MIBS, EPDS, PHQ-9, and GAD-7 (difference between arms at Week 8, controlling for baseline) will be evaluated using the same analysis plan proposed for the analysis of the primary endpoint (HAM-D). In addition, the differences in HAM-D6 scores between baseline and week 8 within each treatment arm will be calculated. Secondary endpoints are not powered to detect a significant difference between treatment groups and no sequential testing will be applied.

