9.8 HANDLING OF MISSING VALUES

According to the schedule of events, patients are expected to attend visits at baseline, Week 4, and Week 8. No explicit imputation will be performed; the MMRM model described above will be run on the ITT population, which implicitly imputes missing data under a missing at random (MAR) assumption.

To examine the impact of intermediate missing values and missing values after early withdrawal from the study, sensitivity analyses including multiple imputations will be performed. Missing safety data will not be imputed.

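### The only visible convergence fallback, a 2-parameter AR(1), forces equal variances at Weeks 4 and 8 and keeps the site random effect; if it is used and the variances differ, the Week 8 test could be miscalibrated

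*Combined protocol and SAP*

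**What the plan says.** Section 9.1 specifies a REML MMRM "parameterized to include random effects for site and repeated measures for post-baseline visits", with an "unstructured residual covariance structure (3 parameters"). The synopsis (Statistical Methods) repeats this. Both places give one contingency. It applies "in the unlikely event that the unstructured covariance matrix fails to converge". What follows in that case, according to both places, is that "the model will be refit with a first order autoregressive covariance matrix (2 parameters"). Nothing else in the model is said to change, so as written the site random effect remains.

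The number of modelled visits follows from Section 9.8: "patients are expected to attend visits at baseline, Week 4, and Week 8". Only Weeks 4 and 8 are post-baseline. The synopsis bases the test on the MMRM, a "model-based t-test with a two-sided significance level of 5" percent. The visible text mentions no empirical standard error. Section 9.2 extends the approach to the four secondary scales, which "will be evaluated using the same analysis plan proposed for the analysis of the primary endpoint (HAM-D").

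**The concern.** A fallback should give up something the primary test can spare. With two visits, this one gives up only the separate variance for Week 8, which is what the standard error of the primary contrast depends on. A model-based test then uses a variance pooled over both visits. It is anti-conservative if scores vary more at Week 8 than at Week 4, and conservative if they vary less.

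The rule also leaves untouched the other covariance component that might be simplified, the site effect. With up to 25 sites and 210 planned participants, sites average 210/25 = 8.4 women. If the rule were used, it would produce the primary p-value. Under Section 9.2 it would also apply to the secondary scales.

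**Working it through.** **Inputs from the documents.** Two post-baseline visits (Section 9.8); unstructured with 3 parameters and AR(1) with 2 (Section 9.1); two-sided 5% model-based t-test (synopsis); 210 participants, 1:1, up to 25 sites (synopsis).

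**Assumed inputs.** The visible text gives no SD by visit, so I vary r = SD at Week 8 / SD at Week 4. For the simulations I also assumed a within-person correlation of 0.6, about 10% missing at Week 4 and about 20% MAR missing at Week 8.

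**Step 1: the plan's parameter counts.** For T = 2 visits, unstructured has T(T+1)/2 = 3 parameters (two variances, one covariance). Homogeneous AR(1) has 2 (one variance, one correlation). Both stated figures reproduce. At T = 2 this AR(1) is the same model as compound symmetry. Heterogeneous AR(1) or heterogeneous compound symmetry would have 3 parameters and be the same model as unstructured. Any simpler residual structure that keeps a correlation must therefore pool the variances.

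**Step 2: effect of pooling, complete data.** The pooled variance is (SD4² + SD8²)/2, while the Week 8 contrast needs SD8². Hence

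reported SE / true SE = √((1 + r²)/2) / r, and type I error = 2 × [1 − Φ(1.96 × ratio)].

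For r = 1.2: √((1 + 1.44)/2)/1.2 = 1.1045/1.2 = 0.920; 1.96 × 0.920 = 1.80; type I error 7.1%.

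For r = 0.85: √((1 + 0.7225)/2)/0.85 = 0.9280/0.85 = 1.092; 1.96 × 1.092 = 2.14; type I error 3.2%.

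| r | SE ratio | Type I error |
|---|---|---|
| 0.70 | 1.23 | 1.6% |
| 0.85 | 1.09 | 3.2% |
| 1.00 | 1.00 | 5.0% |
| 1.10 | 0.96 | 6.1% |
| 1.20 | 0.92 | 7.1% |
| 1.50 | 0.85 | 9.6% |

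**Step 3: simulation with dropout.** REML fits with N = 210, arm and baseline effects by visit, no site effect, and 2,500 to 3,000 trials per case:

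| r | AR(1) mean SE | AR(1) empirical SD | AR(1) type I | Unstructured type I |
|---|---|---|---|---|
| 0.85 | 0.563 | 0.525 | 3.6% | 5.6% |
| 1.00 | 0.601 | 0.592 | 4.8% | 4.6% |
| 1.20 | 0.659 | 0.710 | 6.8% | 4.7% |

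The Monte Carlo standard error at 2,500 trials is √(0.05 × 0.95/2500) = 0.4 percentage points. The unstructured results are compatible with 5%, and the AR(1) results follow the formula.

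**Step 4: the site term.** Smaller runs (60 fits in each of 8 scenarios, 480 in all) added a random intercept for 25 sites. With r = 1.2 and about 20% missing at Week 8, the estimated site variance was effectively zero in about 57% of fits at an intraclass correlation of 0, 38% at 0.02 and 13% at 0.05. The unstructured 2×2 matrix was near-singular in none of the 480. With 60 fits per scenario these percentages are rough.

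**The case against.** The strongest reply is that this rarely matters. The plan calls the trigger unlikely, and a 2×2 matrix estimated from about 210 women should fit. Suppose the fallback fired in 1% to 5% of trials, an assumed range, with 7.1% error when it did. Overall type I error would be 5 + 0.01 × 2.1 = 5.02% to 5 + 0.05 × 2.1 = 5.11%. For the secondary scales, Section 9.2 already disclaims power and sequential testing. This reply stands and sets the weight of the point.

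Three stronger readings are tempting, and the documents do not support them.

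- A reader might infer that the p-value is wrong whenever the fallback is used. It is not: with equal variances AR(1) is correct (simulated error 4.8% at r = 1).
- A reader might infer from the entry limit ("HAM-D6 score > 7 and < 13 at Screening") that spread must grow by Week 8. The limit restricts baseline. Both modelled visits come later and are unrestricted, and improvement towards the scale's floor of 0 could narrow Week 8. The 9.6% figure needs r = 1.5, which nothing visible establishes.
- A reader might infer that the site effect is the likelier cause of failure. The documents do not say so. Step 4 is compatible with fragility there, but a zero site variance is often a boundary solution in a converged fit and may never trigger the rule.

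Text is also missing. Section 9.7 refers to a Model 3 in Section 9.1 that is not visible, and Section 8.1 defers detail to a SAP that is not shown. A site rule or robust standard error there cannot be excluded. Section 8.1 does commit generally to checking assumptions and applying corrective procedures before testing, but it does not say what would be done about unequal variances under the fallback.

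**Conclusion.** The point holds as a conditional one. The visible fallback imposes equal variances at Weeks 4 and 8, leaves the site random effect in place and names no robust standard error. If it is used and the variances differ, the Week 8 standard error is off by about −8% (r = 1.2) to +9% (r = 0.85), and type I error is about 7% or 3% respectively. The direction cannot be known in advance.

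These sizes rest on assumed SD ratios and on the visible text being the whole rule. The parameter counts and the equal-variance constraint need no such assumption. Practical impact is small because the trigger is unlikely; the change is worth making because it is nearly free and the rule, if used, determines the primary result.

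**What to change.** Replace the fallback sentence in Section 9.1 and the synopsis, and align the SAP, with wording such as: *If the model does not converge, the unstructured matrix for Weeks 4 and 8 is kept and the random effect of site is removed. If the model still does not converge, AR(1) is used with empirical (sandwich) standard errors.*

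The order matters. With two visits there is no intermediate residual structure to try (Step 1), so simplification has to come from elsewhere. Removing site first also makes the participant the independent unit, so the sandwich estimator would rest on about 210 units and not on at most 25 sites. AR(1) stays last because a sandwich standard error corrects the reported uncertainty, not any bias from a misspecified covariance when data are missing at random.

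A Week 8-only ANCOVA should not be added as a further step. It would discard Week 4 data from women missing Week 8 and weaken the missing-at-random handling in Section 9.8.

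The cost is a short text change and, only if the contingency arises, the loss of a planned site term.

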9.2 SECONDARY ENDPOINTS

The treatment efficacy of MIBS, EPDS, PHQ-9, and GAD-7 (difference between arms at Week 8, controlling for baseline) will be evaluated using the same analysis plan proposed for the analysis of the primary endpoint (HAM-D). In addition, the differences in HAM-D6 scores between baseline and week 8 within each treatment arm will be calculated. Secondary endpoints are not powered to detect a significant difference between treatment groups and no sequential testing will be applied.

9.3 EXPLORATORY ENDPOINT(S)

Exploratory analyses will be conducted in the ITT population. Given the ordinal nature of the remaining efficacy endpoints (CGI-I; CGI-S; PGI-C; PGI-S), the analysis plan for HAM-D will be modified to compare treatment arms by the odds selecting a given ordinal category at Week 8 controlling for other factors in the model. Models will be fit via PROC GLIMMIX.

Additionally, the MMRM approach to analyzing the difference between arms will be supplemented via a latent class analysis approach that uses a multiple indicator linear growth model (LGM) for categorical outcomes. More details about the analyses can be found in the SAP.

9.4 SAFETY ENDPOINT(S)

AEs and SAEs that may be reported by the participant or detected by the investigator through the C-SSRS will be compared between treatment groups. All safety variables will be summarized descriptively by randomized treatment.

9.5 ANALYSIS OF SAFETY

The Safety Analysis Set will be used for the analysis of AE data.

AEs will be coded with MedDRA. All AEs with an onset date on or after the date of first use of the investigational product and before the date of last use of the investigational device will be collected and presented by system organ class and preferred term in frequency tables. Participants with multiple AEs will be counted only once within each preferred term and system organ class. Key participant information for participants with an AE with an outcome of death, participants with SAEs, and participants with an AE leading to withdrawal from the study will be listed.

Sponsor Name: Woebot Health

Protocol Number: WB001-001

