4.6 STUDY DISCONTINUATION OR WITHDRAWAL

Discontinuation of study treatment for a participant occurs when study treatment is stopped earlier than the protocol planned duration and can be initiated by either the participant or the investigator. The investigator must discontinue study treatment for a given participant if he/she believes that continuation would negatively impact the participant's well-being. Involvement in the study is strictly voluntary. Participants have the right to withdraw from the study at any time for any reason, without any reprisal.

Participants should be discontinued from the study if any of the following occur:

1. The participant withdraws consent to participate in the study
2. The participant develops an illness that would interfere with her continued participation in the study
3. The participant has an SAE rated as Grade 3 (severe) or higher (see [Table 3 Clinical Concerns Categorizations](#))

Sponsor Name: Woebot Health

Protocol Number: WB001-001

4. The participant is noncompliant with treatment schedule, study procedures, in the opinion of the investigator and per the protocol, where applicable
5. The participant is confirmed to be pregnant (by self-report during scheduled assessment with the investigator/qualified site staff at Week 4 and 8)
6. The PI, Sponsor, IRB, or regulatory agency requests withdrawal of the participant
7. Any other reason relating to the participant's safety or integrity of the study data as determined by the DSMB

Participants who withdraw from the study may be replaced. Participants who withdraw or are withdrawn from the study cannot subsequently rejoin the study.

If a participant withdraws or is withdrawn from the study, the study Sponsor, sites, and DSMB will be informed immediately. If there is a medical reason for withdrawal, the participant will remain under the supervision of the investigator until satisfactory health has returned or appropriate referrals have been made and executed upon.

Unless a participant withdraws consent for follow-up procedures, they should continue to attend all scheduled study telehealth visits, including the EOT visit. Even if a participant declines to participate in the remaining scheduled telehealth visits, she will be encouraged to attend an early withdrawal visit, with the same assessments as the Week 8 EOS visit, as indicated in [Appendix 3: SoE](#).

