7.3 SERIOUS ADVERSE EVENTS

An SAE is any AE that meets any of the following criteria:

- Results in death
- Is *life-threatening*
- Requires inpatient *hospitalization* or prolongation of existing hospitalization
- Results in persistent or significant *disability/incapacity*
- Is an *important medical event*

Sponsor Name: Woebot Health

Protocol Number: WB001-001

UNANTICIPATED ADVERSE DEVICE EFFECTS

A suspected unanticipated adverse device effect (UADE) is defined as an untoward and unintended response to a study treatment, which is not listed in the applicable product information, and meets at least one AE or SAE criterion, and is assessed as causally related to the study treatment. The Sponsor or designee will be responsible for carrying out required reporting to investigators, health authorities, and other entities as required by law.

DOCUMENTING AND REPORTING ADVERSE EVENTS AND SERIOUS ADVERSE EVENTS

Reporting of non-serious AEs and SAEs will begin at the time of first interaction with the app and will continue through EOT. Any new clinical condition or worsening of existing conditions between the time the informed consent form (ICF) is signed, and the first use of the study intervention will be recorded as AE/SAEs unrelated to the device.

AEs and SAEs may be reported spontaneously by participants, discovered as a result of general, non-leading verbal questioning by the study staff, or determined by assessments. As needed, qualified study staff will inform investigators to inquire about any new symptoms or worsening of symptoms during the telehealth visits at Weeks 4 and 8. In the interim, participants will be instructed to contact the investigator if new or worsening symptoms develop outside of key assessment visits. All incidences confirmed as AEs or SAEs will be monitored and recorded in the eCRF throughout the entire study.

The investigator must pursue and obtain adequate information about all incidences they deem as AEs and SAEs. At minimum this includes a description of the event, severity, device relatedness, start and stop times, duration, outcome, and any action (e.g., treatment/follow-up tests). The investigator must also assess whether the event meets the criteria for classification as an SAE.

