8.2 ANALYSIS POPULATIONS

For the purposes of analysis, the following analysis sets are defined in [Table 4](#) below.

TABLE 4. SUMMARY OF ANALYSIS SETS

Analysis Set	Description
Enrolled	All participants who signed the ICF
Intention-To-Treat (ITT)	All randomized participants with HAM-D6 measured at baseline. Participants will be included in the ITT population regardless of how often they engage with WB001 or ED001. This analysis set will be the primary set used for analyses/summaries of the primary efficacy endpoint, as well as for all secondary and exploratory efficacy endpoints.
Per-Protocol (PP)	All randomized participants also in the ITT population who complete 8 weeks of treatment and have at least 75% compliance on engaging with the Woebot application at least 1 day per week, and who have HAM-D measured at baseline, Week 4, and Week 8, with no other major protocol deviation that could affect the interpretability of the efficacy outcome. This analysis set will be used for sensitivity analyses.
Safety	All randomized participants who used WB001 or ED001 and who have at least one post-baseline safety assessment (i.e., C-SSRS). This analysis set will be used for summaries of safety data.

*Note: Inclusion criteria at screening will assess for participants engagement in TAU. If participant is confirmed as not having completed TAU by EOT, the data from these patients will be excluded from the primary analysis; however, their data will be retained for the purpose of conducting exploratory analysis.
	

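### By-arm AE tables stop before each woman's last day of app use and leave out women with no post-baseline C-SSRS, although AEs are collected through EOT

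*Combined protocol and SAP*

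**What the plan says.** **Tabulation.** Section 9.5 uses the Safety Analysis Set and puts into the system organ class and preferred term tables only AEs with onset "on or after the date of first use of the investigational product and before the date of last use of the investigational device". Table 4 (Section 8.2) defines that set as randomized women who used either app and "who have at least one post-baseline safety assessment (i.e., C-SSRS").

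**Collection.** Section 7.3 says AE and SAE reporting "will begin at the time of first interaction with the app and will continue through EOT". Appendix 3 also ends collection at the EOT visit, Day 56 ± 3. (The two sections differ on when collection starts, which does not matter here.) Under Section 4.6, unless a woman withdraws consent for follow-up, "they should continue to attend all scheduled study telehealth visits, including the EOT visit".

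**App use.** Table 4 keeps women in the ITT set "regardless of how often they engage with WB001 or ED001". The Per-Protocol set asks only that they "have at least 75% compliance on engaging with the Woebot application at least 1 day per week".

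**Use of the results.** Section 9.4 says AEs and SAEs "will be compared between treatment groups", by randomized arm. Section 9.5 adds that deaths, "participants with SAEs, and participants with an AE leading to withdrawal from the study will be listed".

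**The concern.** The end of the counting window is something each woman does after randomization. Two women followed to the same EOT visit contribute different amounts of countable time if one stops opening her app earlier. The two apps differ, so equal duration of use cannot be taken for granted. If it differs by arm, the tables can show an AE difference that does not exist or hide one that does.

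The cut-off can also be triggered by the event itself. Section 4.6 treats stopping study treatment separately from leaving the study. A woman who stops the app because of a non-serious AE that began that day, and who stays in follow-up, is excluded from the tables by the strict *before*. She is not in the listings either, since they cover AEs leading to withdrawal from the study. The benefit/risk text names worsening of PPD symptoms as the main potential risk, and worsening that begins after app use ends is not counted.

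The Safety set adds a second filter. The first scheduled post-baseline C-SSRS is at Week 4 (Day 28 ± 3). A woman who used the app, reported an AE and left with no C-SSRS at all is in neither numerator nor denominator.

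**Working it through.** The plan states no AE rate, power or expected app use for these tables, so there is no figure of its own to reproduce. The check counts days and then illustrates the effect on incidence.

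**Inputs from the documents.** Onset counts from first use (taken as Day 1) and strictly before last use (Section 9.5). Collection runs to EOT, nominally Day 56 (Section 7.3, Appendix 3). The engagement threshold is 75% of 8 weeks = 6 weeks (Table 4). Planned enrolment is 210 at 1:1, so 105 per arm (Synopsis).

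**Assumed.** Every last-use day and every AE risk below.

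**Step 1: days counted.** With last use on Day L, the counted days are 1 to L − 1, so uncounted days = 56 − (L − 1).

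| Last use (L) | Counted | Uncounted of 56 |
|---|---|---|
| Day 1 | 0 | 56 (100%) |
| Day 14 | 13 | 43 (77%) |
| Day 28 | 27 | 29 (52%) |
| Day 36 | 35 | 21 (38%) |
| Day 42 | 41 | 15 (27%) |
| Day 56 | 55 | 1 (2%) |

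Week 6 is Days 36 to 42. A woman who meets the 75% threshold by using the app in Weeks 1 to 6 only therefore has 21 to 15 days uncounted. If her EOT visit is on Day 59 and her last use on Day 42, 59 − 41 = 18 days (31%) are uncounted.

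**Step 2: effect on tabulated incidence.** With a constant hazard and true 56-day risk R, tabulated incidence = 1 − (1 − R)^((L − 1)/56).

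| True risk, both arms | Arm with L = 56 | Other arm | Tabulated |
|---|---|---|---|
| 10% | 1 − 0.9^(55/56) | L = 28: 1 − 0.9^(27/56) | 9.8% v 5.0% |
| 20% | 1 − 0.8^(55/56) | L = 28: 1 − 0.8^(27/56) | 19.7% v 10.2% |
| 20% | 1 − 0.8^(55/56) | L = 42: 1 − 0.8^(41/56) | 19.7% v 15.1% |
| 40% | 1 − 0.6^(55/56) | L = 28: 1 − 0.6^(27/56) | 39.5% v 21.8% |

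The second row is about 20.7 versus 10.7 women of 105, an apparent ratio of 1.93 with no true difference. If only half of the second arm stopped at Day 28 and the rest continued to Day 56, that arm would show about (19.7 + 10.2)/2 = 15%.

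**Step 3: a real difference hidden.** Take a true 30% on WB001 with last use Day 36, and 20% on ED001 with last use Day 56. The tables show 1 − 0.7^(35/56) = 20.0% versus 1 − 0.8^(55/56) = 19.7%. This lets the excess hazard continue after use stops. If it ended after the 35 counted days, the true WB001 risk would be 1 − 0.7^(35/56) × 0.8^(21/56) = 26.4%, and the hidden gap would be 6.4 points instead of 10.

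**Step 4: Safety set.** If 5% to 30% of women (assumed) had no post-baseline C-SSRS, 10.5 to 63 of 210 would leave the AE tables.

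**The case against.** **App use.** Engagement frequency is not the date of last use. A woman who skips Weeks 3 and 5 also meets 75%, yet can lose only one day; the 27% to 38% loss needs the two missed weeks to be the last two. The plan describes an 8-week treatment period with uninstall instructions at Week 8, so for women who persist, last use and EOT nearly coincide. No document gives a last-use distribution, and one last-use day for a whole arm is extreme. All of this stands: it limits the size of the problem and leaves the direction unknown.

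**Other safeguards.** The C-SSRS and the suicidality items are assessed at scheduled visits regardless of app use. Section 7 requires DSMB review of all AEs and SAEs, and Section 7.4 has the DSMB review safety differences between arms. The listings in Section 9.5 carry no date window. These protect participants during the trial but do not put the missing events into the by-arm tables. The listings give no incidence, and Section 9.5 ties AE analysis to the Safety set, so they may be restricted too.

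**Safety set.** An unscheduled or early-withdrawal C-SSRS would qualify some early leavers, and women with none will often have little AE follow-up. This is fair. The gap that remains is the woman with a spontaneously reported AE and no C-SSRS.

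**Wording.** *Before* may have been meant as *on or before*. That restores one day and leaves the interval from last use to EOT uncounted. On-use counting is a recognised display, but as the only table it discards follow-up that the protocol sets out to obtain. Section 8.1 says the SAP will expand on the methods; nothing in the text reviewed changes this window.

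**Conclusion.** The concern holds. As written, Sections 8.2 and 9.5 remove collected AEs from the between-arm comparison in Section 9.4 according to duration of app use and whether a C-SSRS was obtained. The day counts follow from the wording once a last-use day is assumed: 15 to 21 of 56 days are lost when use ends in Week 6, and the whole window is lost with one-day use. The incidence figures also assume a constant hazard and chosen AE risks, and they show what could happen, not what is expected. If use and retention turn out alike in both arms, AE counts would be low in both without favouring either. Safety is summarized descriptively and the primary analysis is unaffected, so this should be fixed but does not threaten the trial's main conclusion. Confidence is high on the mismatch in the text; the practical bias cannot be sized from the documents.

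**What to change.** - **Section 9.5:** tabulate all AEs and SAEs with onset from first use of either app through the Week 8/EOT or early-termination visit, or last contact, whenever app use ended.
- **Table 4, Section 8.2:** define the Safety set as all randomized women who used WB001 or ED001 at least once. Require a post-baseline C-SSRS only for the C-SSRS summaries.
- **Listings:** state that the listings of deaths, SAEs and AEs leading to withdrawal use the same set and window.
- **Secondary display:** keep on-use counts, so events that began off the app can be seen.
- **Terminology:** use one term covering both apps. Section 1.3 describes only WB001 as the investigational device, and the Synopsis calls ED001 the control device, so the current wording leaves the ED001 window unclear.

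The cost is wording in two sections. No new collection is needed, since AEs are already planned through EOT for women who remain in follow-up; those who withdraw consent for follow-up would be counted to last contact. Reported AE counts may rise, and some added events will have begun after app use stopped.
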